 o Footnote [3] will be same as in 14.2.2.9.2, except changing "5-D Pruritus Scale" to "POEM"
- Repeat for 14.2.2.12.3 Mean Change in POEM Total Score from Baseline to Weeks 2, 4, and 8 Primary Analysis for PP Population
 Footnote [3] will be same as in 14.2.2.9.3, except changing "5-D Pruritus Scale" to "POEM"
- Repeat for 14.2.2.12.4 Mean Change in POEM Total Score from Baseline to Weeks 2, 4, and 8 Sub-Analysis for PP Population
 - Footnote [3] will be same as in 14.2.2.9.4, except changing "5-D Pruritus Scale" to "POEM"

Table 14.2.2.13.1 Proportion of Subjects with ≥50% Improvement in EASI (EASI-50) from Baseline to Weeks 2, 4, and 8 – Primary Analysis (mITT Population)

| Visit | Statistic Type | Statistic | B244 O.D. 5.0 (N=xx) | B244 O.D. 20.0 (N=xx) | Pooled B244 (N=xx) | Vehicle (N=xx) |
|------------|----------------|----------------------------------|------------------------------|------------------------------|------------------------------|------------------------------|
| Week 2 | Logistic [1,2] | n/N (Proportion %) [3] 95% CI | xx/xx (xx.x) (xx.x, xx.x) | xx/xx (xx.x) (xx.x, xx.x) | xx/xx (xx.x) (xx.x, xx.x) | xx/xx (xx.x) (xx.x, xx.x) |
| Domast for | v. Vehicle | Odds Ratio (95% CI) p-value | x.xx (x.xx, x.xx) x.xxxx | x.xx (x.xx, x.xx) x.xxxx | x.xx (x.xx, x.xx) x.xxxx | N/A N/A |
| Weeks 4, 8 | 20.0 v 5.0 | Odds Ratio (95% CI) p-value | N/A N/A | x.xx (x.xx, x.xx) x.xxxx | N/A N/A | N/A N/A |

[1] Logistic regression model contains treatment group as the explanatory variable. All subjects who meet mITT criteria are included and no data is excluded based on rescue medication use.

[2] Treatment response is improvement by \geq 50% in EASI score.

[3] n is the number of subjects who have improved at that visit. N is the number of subjects with data at that visit, regardless of improvement status.

Source: Listing XXXX

PROGRAM NAME: XXXXXXXXXX

DATE: HH:MM/DDMMMYYYY

- Repeat for 14.2.2.13.2 Proportion of Subjects with \geq 50% Improvement in EASI (EASI-50) from Baseline to Weeks 2, 4, and 8 Sub-Analysis for mITT Population
 - Footnote [1] will be same as in 14.2.2.13.1, except changing the last statement to "Excludes visit data collected on/after date of first on-treatment rescue medication use through the end of the study."
 - Footnotes [2,3] will be same as in 14.2.2.13.1
- Repeat for 14.2.2.13.3 Proportion of Subjects with \geq 50% Improvement in EASI (EASI-50) from Baseline to Weeks 2, 4, and 8 Non-Responder Imputation (NRI) Analysis for mITT Population
 - Footnote [1] will be same as in 14.2.2.13.1, except changing the last statement to "Subjects who discontinue treatment early or who take on-treatment rescue medications are imputed as non-responders."
 - Footnotes [2,3] will be same as in 14.2.2.13.1
- Repeat for 14.2.2.13.4 Proportion of Subjects with \geq 50% Improvement in EASI (EASI-50) from Baseline to Weeks 2, 4, and 8 Primary Analysis for PP Population
 - Footnote [1] will be same as in 14.2.2.13.1, except changing the last statement to "All subjects who meet PP criteria are included."
 - Footnotes [2,3] will be same as in 14.2.2.13.1
- Repeat for 14.2.2.13.5 Proportion of Subjects with \geq 50% Improvement in EASI (EASI-50) from Baseline to Weeks 2, 4, and 8 Sub-Analysis for PP Population
 - Footnote [1] will be same as in 14.2.2.13.1, except changing the last statement to "All subjects who meet PP criteria are included."
 - Footnotes [2,3] will be same as in 14.2.2.13.1
- Repeat for 14.2.2.13.6 Proportion of Subjects with ≥50% Improvement in EASI (EASI-50) from Baseline to Weeks 2, 4, and 8 Non-Responder Imputation (NRI) Analysis for PP Population
 - Footnote [1] will be same as in 14.2.2.13.1, except changing the last statement to "Subjects who discontinue treatment early or who take on-treatment rescue medications are imputed as non-responders."
 - Footnotes [2,3] will be same as in 14.2.2.13.1
- Repeat for 14.2.2.14.1 Proportion of Subjects with ≥75% Improvement in EASI (EASI-75) from Baseline to Weeks 2, 4, and 8 Primary Analysis for mITT Population

• Footnotes [1,3] will be same as in 14.2.2.13.1.

.

- Footnote [2] will be same as in 14.2.2.13.1, except changing "50%" to "75%"
- Repeat for 14.2.2.14.2 Proportion of Subjects with \geq 75% Improvement in EASI (EASI-75) from Baseline to Weeks 2, 4, and 8 Sub-Analysis for mITT Population
 - \circ Footnotes [1,3] will be same as in 14.2.2.13.2.
 - Footnote [2] will be same as in 14.2.2.13.1, except changing "50%" to "75%"
- Repeat for 14.2.2.14.3 Proportion of Subjects with ≥75% Improvement in EASI (EASI-75) from Baseline to Weeks 2, 4, and 8 Non-Responder Imputation (NRI) Analysis for mITT Population
 - Footnotes [1,3] will be same as in 14.2.2.13.3.
 - Footnote [2] will be same as in 14.2.2.13.1, except changing "50%" to "75%"
- Repeat for 14.2.2.14.4 Proportion of Subjects with \geq 75% Improvement in EASI (EASI-75) from Baseline to Weeks 2, 4, and 8 Primary Analysis for PP Population
 - \circ Footnotes [1,3] will be same as in 14.2.2.13.4.
 - Footnote [2] will be same as in 14.2.2.13.1, except changing "50%" to "75%"
- Repeat for 14.2.2.14.5 Proportion of Subjects with ≥75% Improvement in EASI (EASI-75) from Baseline to Weeks 2, 4, and 8 Sub-Analysis for PP Population
 - \circ Footnotes [1,3] will be same as in 14.2.2.13.5.
 - Footnote [2] will be same as in 14.2.2.13.1, except changing "50%" to "75%"
- Repeat for 14.2.2.14.6 Proportion of Subjects with ≥75% Improvement in EASI (EASI-75) from Baseline to Weeks 2, 4, and 8 Non-Responder Imputation (NRI) Analysis for PP Population
 - \circ Footnotes [1,3] will be same as in 14.2.2.13.6.
 - Footnote [2] will be same as in 14.2.2.13.1, except changing "50%" to "75%"
 - Repeat for 14.2.2.15.1 Proportion of Subjects with ≥90% Improvement in EASI (EASI-90) from Baseline to Weeks 2, 4, and 8 Primary Analysis for mITT Population • Footnotes [1,3] will be same as in 14.2.2.13.1.
 - Footnote [2] will be same as in 14.2.2.13.1, except changing "50%" to "90%"
- Repeat for 14.2.2.15.2 Proportion of Subjects with ≥90% Improvement in EASI (EASI-90) from Baseline to Weeks 2, 4, and 8 Sub-Analysis for mITT Population
 - \circ Footnotes [1,3] will be same as in 14.2.2.13.2.
 - Footnote [2] will be same as in 14.2.2.13.1, except changing "50%" to "90%"
- Repeat for 14.2.2.15.3 Proportion of Subjects with ≥90% Improvement in EASI (EASI-90) from Baseline to Weeks 2, 4, and 8 Non-Responder Imputation (NRI) Analysis for mITT Population
 - Footnotes [1,3] will be same as in 14.2.2.13.3.
 - Footnote [2] will be same as in 14.2.2.13.1, except changing "50%" to "90%"
- Repeat for 14.2.2.15.4 Proportion of Subjects with \geq 90% Improvement in EASI (EASI-90) from Baseline to Weeks 2, 4, and 8 Primary Analysis for PP Population
 - \circ Footnotes [1,3] will be same as in 14.2.2.13.4.
 - Footnote [2] will be same as in 14.2.2.13.1, except changing "50%" to "90%"
- Repeat for 14.2.2.15.5 Proportion of Subjects with ≥90% Improvement in EASI (EASI-90) from Baseline to Weeks 2, 4, and 8 Sub-Analysis for PP Population
 - \circ Footnotes [1,3] will be same as in 14.2.2.13.5.
 - Footnote [2] will be same as in 14.2.2.13.1, except changing "50%" to "90%"
- Repeat for 14.2.2.15.6 Proportion of Subjects with \geq 90% Improvement in EASI (EASI-90) from Baseline to Weeks 2, 4, and 8 Non-Responder Imputation (NRI) Analysis for PP Population
 - \circ Footnotes [1,3] will be same as in 14.2.2.13.6.
 - Footnote [2] will be same as in 14.2.2.13.1, except changing "50%" to "90%"
- Repeat for 14.2.2.16.1 Proportion of Subjects with IGA of Clear or Almost Clear and ≥2 Point Improvement from Baseline to Weeks 2, 4, and 8 Primary Analysis for mITT Population
 - Footnotes [1,3] will be same as in 14.2.2.13.1.
 - Footnote [2]: Treatment response is improvement by ≥ 2 Points in IGA score to Clear or Almost Clear.

- Repeat for 14.2.2.16.2 Proportion of Subjects with IGA of Clear or Almost Clear and ≥2 Point Improvement from Baseline to Weeks 2, 4, and 8 Sub-Analysis for mITT Population
 - Footnotes [1,3] will be same as in 14.2.2.13.2.
 - Footnote [2] will be same as in 14.2.2.16.1.
- Repeat for 14.2.2.16.3 Proportion of Subjects with IGA of Clear or Almost Clear and ≥2 Point Improvement from Baseline to Weeks 2, 4, and 8 Non-Responder Imputation (NRI) Analysis for mITT Population
 - \circ Footnotes [1,3] will be same as in 14.2.2.13.3.
 - Footnote [2] will be same as in 14.2.2.16.1.
- Repeat for 14.2.2.16.4 Proportion of Subjects with IGA of Clear or Almost Clear and ≥2 Point Improvement from Baseline to Weeks 2, 4, and 8 Primary Analysis for PP Population
 - Footnotes [1,3] will be same as in 14.2.2.13.4.
 - Footnote [2] will be same as in 14.2.2.16.1.
- Repeat for 14.2.2.16.5 Proportion of Subjects with IGA of Clear or Almost Clear and ≥2 Point Improvement from Baseline to Weeks 2, 4, and 8 Sub-Analysis for PP Population
 - \circ Footnotes [1,3] will be same as in 14.2.2.13.5.
 - Footnote [2] will be same as in 14.2.2.16.1.
- Repeat for 14.2.2.16.6 Proportion of Subjects with IGA of Clear or Almost Clear and ≥2 Point Improvement from Baseline to Weeks 2, 4, and 8 Non-Responder Imputation (NRI) Analysis for PP Population
 - \circ Footnotes [1,3] will be same as in 14.2.2.13.6.
 - Footnote [2] will be same as in 14.2.2.16.1.
- Repeat for 14.2.2.17.1 Proportion of Subjects with IGA of Clear or Almost Clear at Weeks 2, 4, and 8 Primary Analysis for mITT Population
 - \circ Footnotes [1,3] will be same as in 14.2.2.13.1.
 - Footnote [2]: Treatment response is improvement by ≥ 2 Points in IGA score.
- Repeat for 14.2.2.17.2 Proportion of Subjects with IGA of Clear or Almost Clear at Weeks 2, 4, and 8 Sub-Analysis for mITT Population
 - \circ Footnotes [1,3] will be same as in 14.2.2.13.2.
 - Footnote [2] will be same as in 14.2.2.17.1.
- Repeat for 14.2.2.17.3 Proportion of Subjects with IGA of Clear or Almost Clear at Weeks 2, 4, and 8 Non-Responder Imputation (NRI) Analysis for mITT Population
 - Footnotes [1,3] will be same as in 14.2.2.13.3.
 - Footnote [2] will be same as in 14.2.2.17.1.
- Repeat for 14.2.2.17.4 Proportion of Subjects with IGA of Clear or Almost Clear at Weeks 2, 4, and 8 Primary Analysis for PP Population
 - \circ Footnotes [1,3] will be same as in 14.2.2.13.4.
 - Footnote [2] will be same as in 14.2.2.17.1.
- Repeat for 14.2.2.17.5 Proportion of Subjects with IGA of Clear or Almost Clear at Weeks 2, 4, and 8 Sub-Analysis for PP Population
 - Footnotes [1,3] will be same as in 14.2.2.13.5.
 - Footnote [2] will be same as in 14.2.2.17.1.
- Repeat for 14.2.2.17.6 Proportion of Subjects with IGA of Clear or Almost Clear at Weeks 2, 4, and 8 Non-Responder Imputation (NRI) Analysis for PP Population
 - \circ Footnotes [1,3] will be same as in 14.2.2.13.6.
 - Footnote [2] will be same as in 14.2.2.17.1.
- Repeat for 14.2.2.18.1 Proportion of Subjects with Any IGA Improvement from Baseline to Weeks 2, 4, and 8 Primary Analysis for mITT Population
 - Footnotes [1,3] will be same as in 14.2.2.13.1.
 - \circ Footnote [2]: Treatment response is any improvement in IGA score. Any improvement is defined as ≥ 1 point improvement from Baseline.
 - Repeat for 14.2.2.18.2 Proportion of Subjects with Any IGA Improvement from Baseline to Weeks 2, 4, and 8 Sub-Analysis for mITT Population
 - \circ Footnotes [1,3] will be same as in 14.2.2.13.2.
 - Footnote [2] will be same as in 14.2.2.18.1.

- Repeat for 14.2.2.18.3 Proportion of Subjects with Any IGA Improvement from Baseline to Weeks 2, 4, and 8 Non-Responder Imputation (NRI) Analysis for mITT Population
 - Footnotes [1,3] will be same as in 14.2.2.13.3.
 - Footnote [2] will be same as in 14.2.2.18.1.
- Repeat for 14.2.2.18.4 Proportion of Subjects with Any IGA Improvement from Baseline to Weeks 2, 4, and 8 Primary Analysis for PP Population
 - \circ Footnotes [1,3] will be same as in 14.2.2.13.4.
 - Footnote [2] will be same as in 14.2.2.18.1.
- Repeat for 14.2.2.18.5 Proportion of Subjects with Any IGA Improvement from Baseline to Weeks 2, 4, and 8 Sub-Analysis for PP Population
 - \circ Footnotes [1,3] will be same as in 14.2.2.13.5.
 - Footnote [2] will be same as in 14.2.2.18.1.
- Repeat for 14.2.2.18.6 Proportion of Subjects with Any IGA Improvement from Baseline to Weeks 2, 4, and 8 Non-Responder Imputation (NRI) Analysis for PP Population
 - \circ Footnotes [1,3] will be same as in 14.2.2.13.6.
 - Footnote [2] will be same as in 14.2.2.18.1.

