6.3 Data Presentation Conventions

The data analysis will be conducted on all participant data when the trial ends. Subjects will be pooled across all sites. Data will be presented by treatment group and pooled B244 treatment.

All data collected will be documented using summary tables, figures, and/or patient data listings.

Continuous variables (e.g., age) are summarized using descriptive statistics (the number of subjects with available data, the mean, standard deviation (SD), median, minimum and maximum). Categorical variables (e.g., race) are summarized using counts and percentages. Percentages are calculated using the total subjects per treatment group.

The following conventions are applied to all data presentations and summaries:

• For continuous variables, all mean and median values are formatted to one more decimal place than the measured value. Standard deviation values are formatted to two more decimal places than the measured value. Minimum and maximum values are presented with the same number of decimal places as the measured value.

STATISTICAL ANALYSIS PLAN

Version 3.0 12-Jan-22

- For categorical variables, the number and percentage of responses are presented in the form XX (XX.X %) where the percentage is in the parentheses.
- Date variables are formatted as DDMMMYYYY for presentation. Time is formatted in military time as HH:MM for presentation.
- P-values, if applicable, will be presented to 4 decimal places. If the p-value is less than 0.0001 then it will be presented as <0.0001.

The statistical test for the primary endpoint will use a one-sided 90% CI. All other statistical tests performed will use a two-sided 95% CI.

The table and listing shells and table of contents as part of this SAP provide the expected layout and titles of the tables, listings, and figures. Any changes to format, layout, titles, numbering, or any other minor deviation will not necessitate a revision to the SAP nor will it be considered a deviation from planned analyses. Only true differences in the analysis methods or data handling will necessitate such documentation. The appropriate listings supporting the tables will be included and are not specified in the individual sections throughout the document.

6.4 **Baseline Definition**

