7 STATISTICAL ANALYSES

7.1 Sample Size Determination

Approximately 576 subjects may be enrolled to account for 16.7% drop out rate prior to completing the study. A total of 160 evaluable subjects per group (480 total) are required to achieve at least 80% power to detect a pairwise difference of 0.65 in mean WI-NRS change from Baseline to Week 4 between one of two active doses of B244 and vehicle control when assuming a standard deviation of 2.5 and applying a Dunnett Testing Method at a one-sided familywise error rate of 0.10.

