7.4.1 Analysis of WI-NRS and AI-NRS

The primary endpoint of mean change from Baseline to Week 4 in WI-NRS will be analyzed using analysis of covariance (ANCOVA) models.

In addition, the continuous efficacy endpoints WI-NRS, AI-NRS will be summarized using descriptive statistics at Baseline, Week 1, Week 2, Week 3, Week 4, Week 5, Week 6, Week 7, and Week 8 for actual values and change from Baseline values.

The difference in treatment groups in change from Baseline values at post-baseline visits will be analyzed using a mixed model with repeated measures to account for within subject variability and including visit (Baseline vs. Week 1, Week 2, Week 3, Week 4, Week 5, Week 6, Week 7, Week 8), treatment group, visit-by-treatment interaction, and Baseline value as explanatory variables. The subject variability will be modelled using a compound symmetry covariance matrix. Other types of covariance structure may be applied should they provide a better model fit.

The frequency and rate of WI-NRS and AI-NRS responders at Week 1, Week 2, Week 3, Week 4, Week 5, Week 6, Week 7, Week 8 (\geq 4 point change from Baseline in WI-NRS and AI-NRS) and other responder endpoints (any improvement from Baseline in WI-NRS and AI-NRS, defined as \geq 1 point change from Baseline) will be reported and compared between treatment groups using a logistic regression model by week. Generalized estimating equations to account for repeated measures and within-subject variability may also be applied. Responder status varies by outcome measure, endpoint, and visit. That is, a subject can be considered a responder at one visit, but not the next for a specific measure. Similarly, a subject can be considered a responder for one measure but not another at the same visit.

Additionally, daily WI-NRS and AI-NRS scores will be presented in by-subject data listings.

7.4.2 Analysis of Primary Endpoint of Change from Baseline to Week 4 in Weekly Average WI-NRS

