The ANCOVA model for the primary endpoint change from Baseline to Week 4 in weekly average WI-NRS will have treatment group and Baseline weekly average WI-NRS as explanatory variables. Hypothesis testing will be done using a Dunnett Testing Method, applying pairwise comparisons of each respective B244 dose group to vehicle using a one-sided familywise error rate of 0.10. Treatment effect will be estimated as least squares means using vehicle as reference and adjusted for multiplicity according to the Dunnett Testing Method and presented with one-sided 90% CI.

Additionally, the two B244 dose groups will be compared by presenting the treatment difference estimated using least squares means.

Finally, in a separate analysis, the pooled B244 dose groups will be compared to vehicle using the same ANCOVA model.

STATISTICAL ANALYSIS PLAN

Version 3.0 12-Jan-22

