 - Footnote [3] will be same as in 14.2.2.3.8, except changing "WI-NRS" to "AI-NRS"

Table 14.2.2.5.1 Proportion of Subjects with ≥4 Point Improvement in WI-NRS from Baseline to Weeks 1 Through 8 – Primary Analysis (mITT Population)

| Visit | Statistic Type | Statistic | B244 O.D. 5.0 (N=xx) | B244 O.D. 20.0 (N=xx) | Pooled B244 (N=xx) | Vehicle (N=xx) |
|-------------|----------------|----------------------------------|------------------------------|------------------------------|------------------------------|------------------------------|
| Week 1 | Logistic [1,2] | n/N (Proportion %) [3] 95% CI | xx/xx (xx.x) (xx.x, xx.x) | xx/xx (xx.x) (xx.x, xx.x) | xx/xx (xx.x) (xx.x, xx.x) | xx/xx (xx.x) (xx.x, xx.x) |
| Papart for | v. Vehicle | Odds Ratio (95% CI) p-value | x.xx (x.xx, x.xx) x.xxxx | x.xx (x.xx, x.xx) x.xxxx | x.xx (x.xx, x.xx) x.xxxx | N/A N/A |
| Weeks 2 – 8 | 20.0 v 5.0 | Odds Ratio (95% CI) p-value | N/A N/A | x.xx (x.xx, x.xx) x.xxxx | N/A N/A | N/A N/A |

[1] Logistic regression model contains treatment group as the explanatory variable. At least one WI-NRS daily score is reported between Days -7 and -1 and for the corresponding week. All subjects who meet mITT criteria are included and no data is excluded based on rescue medication use.

[2] Treatment response is improvement by \geq 4 Points in WI-NRS score (i.e., decrease in WI-NRS score by at least 4 points from Baseline to Post-Baseline visit).

[3] n is the number of subjects who have improved at that visit. N is the number of subjects with data at that visit, regardless of improvement status.

Source: Listing XXXX

PROGRAM NAME: XXXXXXXXXX

DATE: HH:MM/DDMMMYYYY

- Repeat for 14.2.2.5.2 Proportion of Subjects with ≥4 Point Improvement in WI-NRS from Baseline to Weeks 1 Through 8 Primary Analysis Sensitivity for mITT Population
 - o Footnote [1] will be same as in 14.2.2.5.1, except changing "one WI-NRS daily score is" to "four WI-NRS daily scores are"
 - Footnotes [2,3] will be same as in 14.2.2.5.1
- Repeat for 14.2.2.5.3 Proportion of Subjects with ≥4 Point Improvement in WI-NRS from Baseline to Weeks 1 Through 8 Sub-Analysis for mITT Population
 - Footnote [1] will be same as in 14.2.2.5.1, except changing the last statement to "Excludes data collected from the week of first on-treatment rescue medication use through the end of the study. Data collected prior to the week of first on-treatment rescue medication use will be included."

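### The responder logistic models leave out the baseline score that the ANCOVA and MMRM adjust for: a valid test, but some precision is forgone at almost no saving

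*SAP*

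**What the plan says.** SAP 7.4.1 says that the 4-point and any-improvement responders on WI-NRS and AI-NRS will be "compared between treatment groups using a logistic regression model by week". It names no covariate, and neither do SAP 7.4.3 (EASI and IGA responders) or Protocol 12.5. The shells settle the matter. Footnote 1 of Table 14.2.2.5.1 reads "Logistic regression model contains treatment group as the explanatory variable", and the WI-NRS and AI-NRS repeats inherit it. Table 14.2.2.13.1 and its EASI and IGA repeats use the same sentence, as do the addendum's LOCF shells (Tables 14.2.2.5.13 and 14.2.2.14.7). Response on WI-NRS is a "decrease in WI-NRS score by at least 4 points from Baseline to Post-Baseline visit".

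The continuous analyses of the same scales are specified differently. Under SAP 7.4.2 the primary ANCOVA "will have treatment group and Baseline weekly average WI-NRS as explanatory variables", and the MMRM in SAP 7.4.1 and its shells also contain the baseline value.

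SAP 7.4 allows covariates to be added post hoc if the stratified summaries show clear differences. The listed stratifiers include baseline IGA and EASI but not baseline WI-NRS or AI-NRS. The same section says that secondary and exploratory p-values are to be read as exploratory.

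**The concern.** The plan adjusts for baseline while the score is continuous and drops the adjustment once it is dichotomised, without giving a reason. Baseline can be expected to bear on response:

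- **WI-NRS.** The scale runs from 0 to 10 and entry requires a weekly average of at least 6. A 4-point fall therefore means reaching 2 from a baseline of 6, but only 6 from a baseline of 10.
- **AI-NRS.** Eligibility sets no floor. A subject whose baseline is below 4 cannot be a 4-point responder.
- **IGA.** Entry is 2 or 3. Clear or almost clear is one step from 2 and two steps from 3. With the added 2-point requirement, a subject entering at 2 must reach 0.

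At stake are the precision of the responder odds ratios, including the first-listed secondary endpoint, and their exposure to chance baseline differences between arms. The primary conclusion is not at stake.

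**Working it through.** **What the plan gives.** It states no power for any responder endpoint. SAP 7.1 says that 160 evaluable subjects per group "are required to achieve at least 80% power" "to detect a pairwise difference of 0.65 in mean WI-NRS change", with SD 2.5, "applying a Dunnett Testing Method at a one-sided familywise error rate of 0.10"; that concerns the primary endpoint only. The group size agrees with the enrolment target: 576 × (1 − 0.167) = 479.8, or about 480 in three groups. For other tests SAP 6.3 says "All other statistical tests performed will use a two-sided 95% CI", so responder power is taken at two-sided 0.05.

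**Inputs from the documents.** 160 per arm; SD of change 2.5; baseline confined to 6–10; response defined as a fall of at least 4.

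**Assumed inputs.** Baseline is centred at 8 with SD 0.88 (a truncated normal) or 1.15 (nearly flat on 6–10). Mean vehicle improvement m is 1.5 or 2.5. The treatment shift d is 0.65 or 1.0. The slope g of improvement on baseline runs from 0 to 1. Errors are normal. At g = 1 the Week 4 score does not depend on baseline, so this is a strong case.

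**Model.** Improvement = m + g × (baseline − 8) + d × treatment + error, with the error variance set so that the total SD stays at 2.5.

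- Response rate ≈ 1 − Φ((4 − m − d)/2.5). On vehicle (d = 0), m = 1.5 gives 1 − Φ(1.0) = 15.9% and m = 2.5 gives 1 − Φ(0.6) = 27.4%.
- Share of change variance explained by baseline = g² × SD² / 6.25. At g = 1 this is 0.88²/6.25 = 12%, or 21% for the flat distribution.

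**Check of the unadjusted power by formula.** For 27.4% against 36.7%, the SE of the difference is √((0.274 × 0.726 + 0.367 × 0.633)/160) = 0.052. Then 0.093/0.052 ≈ 1.79, and power ≈ Φ(1.79 − 1.96) ≈ 43%, in line with the simulated values below.

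**Simulated power (%), one dose against vehicle, treatment only → with baseline; 4,000 trials per cell, Wald test.**

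| Baseline SD, g | m 1.5, d 0.65 | m 1.5, d 1.0 | m 2.5, d 0.65 | m 2.5, d 1.0 |
|---|---|---|---|---|
| 0.88, 0 | 36.9 → 36.6 | 70.5 → 70.2 | 40.5 → 40.9 | 78.6 → 78.1 |
| 0.88, 0.3 | 36.7 → 36.6 | 71.8 → 72.2 | 42.8 → 43.0 | 77.9 → 78.3 |
| 0.88, 0.5 | 35.1 → 35.4 | 70.1 → 70.3 | 42.6 → 43.3 | 79.6 → 79.9 |
| 1.15, 0.5 | 36.5 → 37.4 | 70.2 → 71.3 | 42.5 → 43.4 | 78.5 → 79.2 |
| 0.88, 1.0 | 36.4 → 37.8 | 71.3 → 73.7 | 43.0 → 45.9 | 79.1 → 81.7 |
| 1.15, 1.0 | 36.8 → 40.5 | 70.4 → 76.2 | 42.3 → 47.2 | 78.6 → 84.5 |

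For g up to 0.5 the change lies between −0.5 and +1.2 points, which is within simulation error or close to it. At g = 1 it is +1.3 to +2.8 points with SD 0.88 and +3.7 to +5.9 with the flat baseline. Gains come from unrounded counts, so they can differ from the table by 0.1.

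**Other scales, also on assumed inputs.** AI-NRS with baseline mean 6.3, SD 1.5 and slopes 0.25–0.75 gained 1.1 to 5.6 points. IGA 0/1 with vehicle response of 35–40% from IGA 2 and 10–15% from IGA 3, and an odds ratio of 2, gained 2.0 to 7.9 points. EASI responders were not simulated.

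**Chance imbalance.** The between-arm baseline difference has SE 0.88 × √(2/160) ≈ 0.10, so a two-SE imbalance is about 0.2 points. At fitted log-odds slopes of 0.34 to 0.73 per baseline point, the odds ratio moves by a factor of exp(0.34 × 0.2) = 1.07 to exp(0.73 × 0.2) = 1.16. For scale, the SE of the log odds ratio at 27.4% against 36.6% is √(1/(160 × 0.274 × 0.726) + 1/(160 × 0.366 × 0.634)) ≈ 0.24. A one-SE imbalance moves the log odds ratio by only about 0.03 to 0.07.

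**The case against.** The case for leaving the models alone has substance. Randomisation makes the treatment-only test valid: its simulated type I error was 4.8–5.2%. Its confidence interval already covers ordinary baseline imbalance, and SAP 7.3.3 tabulates baseline scores by arm, so a large imbalance would be seen. No decision rests on these p-values. All of this stands, and it keeps the point small.

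A reader might infer that baseline largely decides who achieves a 4-point fall. The documents do not support that. They give no correlation or responder rate, and on the 6–10 range baseline explains 0–5% of the variance of change for slopes up to 0.5 and 12–21% at slope 1. A reader might also infer that the trial wastes power it already has. No power is stated for a responder endpoint, and the one powered analysis already adjusts for baseline.

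Two objections bear on the remedy. Adjustment turns a marginal odds ratio into a conditional one: in the slope-1, 1.0-point-shift case the median moved from 1.92 to 2.05 on the same data. It then no longer matches the printed proportions. The room-to-fall argument also carries over poorly to the percentage-based EASI thresholds and to a 1-point WI-NRS fall. The strictest IGA endpoint may have too few responders for a stable adjusted fit. Both objections shape the fix.

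The post-hoc route in SAP 7.4 is only a partial answer. It is optional, is triggered by the data, and does not list baseline WI-NRS or AI-NRS among its stratifiers.

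**Conclusion.** The point holds as a modest refinement. The responder models are inconsistent with the plan's own handling of the same scales, and prespecifying baseline is the better choice. For the 4-point WI-NRS responder the gain is about 0 to 1 point of power under weak or moderate dependence. Under strong dependence it is 1.3 to 5.9 points, mostly about 2.5 to 6. These figures rest on an assumed baseline spread, slope, vehicle improvement and treatment shift, so confidence in the size is moderate; confidence that baseline is omitted is high. The primary analysis is untouched, and no conclusion would be invalid if the models stayed as written.

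**What to change.** Amend SAP 7.4.1, 7.4.3, the responder shells and the addendum's LOCF responder shells as follows:

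1. Include the baseline value of the same scale as a covariate in the WI-NRS and AI-NRS responder models, and in the EASI and IGA responder models. Apply the same rule to any GEE version.
2. Prespecify a fallback to the unadjusted model where responders are too few, with the threshold written down before unblinding. IGA 0/1 with at least a 2-point improvement is the likely case.
3. State that the adjusted odds ratio is conditional on baseline, and keep the unadjusted proportions and unadjusted odds ratio beside it.

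The cost is one term per model, one extra line per table and no new data. The one real drawback is that the adjusted odds ratio will not correspond exactly to the crude proportions, which is why the unadjusted figures should stay. If the analyses have already been run, the adjusted models can be added as supportive and labelled post hoc.
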